IP administration ⁿ	X	QW from Weeks 1 to 23			QW from Weeks 24 ^o to 47								Dosing window is ±2 days; however for QW dosing, every effort should be made to take IP on the same day of the week and must be at least 5 days between 2 doses. IP will be administered SC to the abdomen by trained and qualified study personnel, site staff at clinic visit(s), or at home by healthcare professional, or subject's caregiver for home administration. IP may also be self-administered at the subject's home. o. Week 26 may be an in-clinic or a remote/home visit by healthcare professional who will administer the IP.	
PK blood collection ^p		B	B	B	B		B			B	X	X		p. PK blood samples will be collected predose. Additional blood samples for PK analysis may be collected if clinically indicated (e.g., in case of SAE). For PK sample collection instruction/procedures, refer to the relevant manual.
ELF panel, Pro-C3, adiponectin, FIB-4 index (derived calculation), and adipo-IR (fasting free fatty acids x fasting insulin)	B			X		X			X	X	X			Refer to Appendix 2 (Section 10.2).
Night-time salivary cortisol (NSC) ^q	X ^q				X		X			X	X	X		q. NSC sample will be collected by subject at home between 8:00pm and 12:00am before submitting the sample for processing at the specified visit. If the sample is not collected between 8:00pm and 12:00am, the test should be repeated. The screening assessment should be performed as early as possible during the screening period. Subjects should be provided with

Assessments	Screening Period ¹	Treatment Period										FU Period	Notes:
		Main Study					Extension Study						
Study Day		1 ²											
Study Weeks	-12 to 0		4 ³	8 ⁴	12 ³	16 ⁴	24 ³	26 ⁵	30 ⁴	38 ³	48 ³	ET ^{3,6}	51 ⁷ /EOS
Visit window (days)			±2	±7	±7	±7	+7	+7	±7	±14	+14		±14
													NSC collection kit at the first screening visit, when possible, to allow sample collection return at the following clinic visit. If screening value is >15 nmol/L, Medical Monitor (or designee) may request further workup should the value be of clinical concern; however, values >15 nmol/L will not be exclusionary. The screening NSC is a safety assessment, and not an I/E criteria. Refer to Section 10.2 for further requirements for values >15 nmol/L on treatment (Section 10.2).

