 - a. Unstable angina, myocardial infarction, coronary artery bypass graft (CABG) surgery, percutaneous coronary intervention (PCI), transient ischemic attack (TIA) or cerebrovascular accident (CVA) within 6 months prior to Screening.
 - b. Symptomatic valvular or other structural heart disease.
 - c. Symptomatic congestive heart failure.
 - d. Symptomatic, uncontrolled or high-risk arrhythmia or genetic predisposition to high-risk arrhythmia in the subject or a first degree relative.
 - e. Implanted defibrillator or pacemaker.
 - f. High risk abdominal aortic aneurysm, uncontrolled peripheral vascular disease, or symptomatic carotid stenosis.
8. Uncontrolled or newly diagnosed (<2 months since diagnosis at time of Screening) **hypertension**. Subjects with well controlled hypertension who are clinically stable may enroll if they have been on a stable dose of antihypertensive medications for at least 2 months before Screening.
9. Uncontrolled or newly diagnosed **thyroid disease**. Subjects with treated thyroid disease may be enrolled if they are considered stable on treatment for at least 3 months by the Investigator. Modest dose adjustments per standard of care are allowed.
10. Uncontrolled or newly diagnosed (≤ 3 months since diagnosis) **T2DM**⁹:
 - a. Subjects must have HbA1c level $\leq 9.5\%$ at screening.
 - b. Subjects must have been on a stable antidiabetic regimen for at least 3 months (for insulin and dipeptidyl peptidase IV [DPP-IV] antagonists) or 6 months (for glucagon-like peptide 1 [GLP-1] agonists and sodium glucose co-transporter 2 [SGLT2] inhibitors) prior to biopsy (historical or screening) and remains stable up to randomization. Stable regimen is defined as no addition or discontinuation of antidiabetic medications, but dose adjustments or switching to another medication in the same class at the same relative dose per standard of care are allowed. Thiazolidinediones are not allowed. Subjects on any other antidiabetic regimen not specified above should be on stable treatment for at least 3 months prior to their qualifying biopsy. Consult with the Medical Monitor if further clarification is needed.
11. Type 1 Diabetes Mellitus.

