6.7. Concomitant Therapy

Any medication (including over-the-counter or prescription medicines, vitamins, and herbal supplements) or vaccine that the subject is receiving at the time of enrollment or receives during the study must be recorded along with at least the following information:

- Reason for use
- Dates of administration including start and end dates
- Dosage information including dose and frequency and route of administration

It has previously been reported that NAFLD is associated with reduced CYP3A drug metabolism activity *in vivo* and hepatic CYP3A4 expression in humans ([Woolsey, 2015](#)). In addition, based on the work by Woolsey et al it is suggested that exogenously administered FGF21 may decrease hepatic CYP3A4 activity ([Woolsey, 2016](#)). The underlying mechanism has not been fully elucidated.

Subjects receiving concomitant administration of CYP3A4 substrates with narrow therapeutic index should be closely monitored for any potentially related safety events, and dose adjustment of the CYP3A4 substrate should be considered as needed.

Short-term use of sliding scale insulin therapy during a medical procedure or hospitalization (<5 days) for subjects with T2DM may be performed as needed.

The Medical Monitor (or designee) should be contacted if there are any questions regarding concomitant or prior therapy.

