6.7.1. Prohibited Medications/Therapies

Prohibited therapies include:

- Bariatric surgery
- Elective bone surgery for any bone disorders
- Medications historically associated with secondary NAFLD requiring >2 weeks of pharmacologic dosing . These include amiodarone, methotrexate, glucocorticoids,

tetracyclines, tamoxifen, estrogens or anabolic steroids at doses greater than those used for hormone replacement.

- Other hepatotoxic agents including but not limited to, nefazodone, isoniazid, valproate, and carbamazepine.
- The TNF (tumor necrosis factor) antagonists, adalimumab, etanercept and certolizumab, infliximab or sulfasalazine are prohibited during the Main Study but may be considered for managing emerging AEs in the Extension Study.
 - Short-term oral steroid bursts with/without taper as well as topical and inhaled corticosteroids are allowed.
- Antidiabetic medications: Thiazolidinediones (e.g., pioglitazone) are prohibited throughout study to minimize risk of confounding effect with pegozafermin treatment. Dose adjustments or switching from one medication to another within the same drug class are allowed after randomization for DPP-IV inhibitors (“gliptins”), SGLT2 inhibitors (“gliflozins”) and GLP-1 agonists (“glutides”, including semaglutide [Ozempic]); However, initiation of new DPP-IV inhibitors, SGLT2 inhibitors, or GLP-1 agonists is not allowed during screening and the Main Study (e.g., switching from a DPP-IV inhibitor to a GLP-1 agonist is not allowed, but switching from one DPP-IV inhibitor to another DPP-IV inhibitor is allowed). Initiation of these agents for uncontrolled hyperglycemia (but not for weight loss) may be allowed during the Extension Study with the Medical Monitor’s approval.
- Vitamin E (> 400 IU/day) should not be initiated, or dose increased during the study.
- Any investigational product, FGF21 analogs (e.g., LY2405319, LY3025876, BMS-986036, BMS-986171, PF-05231023, AKR-001, pegozafermin), or FGFR1-activating products. Note: study participants will not be allowed to participate in other interventional trials for FGF21 analog or FGFR1 activating products, during the immunogenicity follow up period.
- Weight loss medications (including GLP-1 agonists specifically for weight loss) should not be initiated during the study.

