8.5.1.2. Homeostatic Model Assessment for Insulin Resistance (HOMA-IR)

HOMA-IR is a method used to quantify insulin resistance based on the following formula(s) (Matthews, 1985):

$$\text{HOMA-IR} = \frac{\text{Glucose} \times \text{Insulin}}{22.5} \quad \text{Glucose in mmol/L}$$
$$\text{HOMA-IR} = \frac{\text{Glucose} \times \text{Insulin}}{405} \quad \text{Glucose in mg/dL}$$

HOMA-IR will be calculated by the central laboratory based on fasting glucose and insulin.

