7.8.3. Exploratory Efficacy Analysis

All other exploratory efficacy endpoints listed in Section 4.1.6 will be analyzed based on Full Analysis Set with confirmed fibrosis stage F2 or F3 and NAS ≥ 4 at baseline per 3-panel consensus read unless otherwise specified. Subject FAST score defined below will also be analyzed.

$$\text{FAST} = \{\exp(-1.65 + 1.07 \times \ln(\text{LSM}) + 2.66 \times 10^{-8} \times \text{CAP}^3 - 63.3 \times \text{AST}^{-1})\} / \{1 + \exp(-1.65 + 1.07 \times \ln(\text{LSM}) + 2.66 \times 10^{-8} \times \text{CAP}^3 - 63.3 \times \text{AST}^{-1})\}$$

For all proportion endpoints, the same stratified CMH methodology as the analysis of primary efficacy endpoints (described in Section 7.8.1) will be used to compare the differences of responder rate in each pegozafermin group versus placebo.

For change from baseline and percent change from baseline endpoints listed Section 4.1.6, descriptive summaries of absolute value and change from baseline at Week 24 will be provided. If there is only a single scheduled post-baseline assessment in Main Study, change from baseline will be analyzed by analysis of variance (ANCOVA) with treatment group, baseline measurement, and two stratification factors as covariates. Otherwise, MMRM method will be used as described in Section 7.8.2. Same as secondary efficacy endpoints, non-parametric van Elteren test stratified by T2DM status (yes vs. no) and fibrosis stage (F2 vs. F3) will be performed if the MMRM (ANCOVA) model assumptions are severely violated. The location shift estimate, and Hodges-Lehmann 2-tailed 95% confidence interval will be presented. For the comparison between each pegozafermin group and placebo, if small cell counts (<5) render the van Elteren test inappropriate, the un-stratified Wilcoxon rank-sum test will be used instead.

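### Fasting insulin, HOMA-IR and Adipo-IR are analysed without a rule for insulin-treated subjects, so insulin dose changes that differ between arms could appear as a change in insulin resistance

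*Protocol*

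**What the plan says.** **Eligibility.** Protocol 5.2, exclusion 10b, admits insulin users: "Subjects must have been on a stable antidiabetic regimen for at least 3 months (for insulin and dipeptidyl peptidase IV". Stability before randomization is loosely defined: "Stable regimen is defined as no addition or discontinuation of antidiabetic medications, but dose adjustments" remain possible.

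**On study.** Protocol 6.7.1 prohibits thiazolidinediones and restricts new starts of three other classes in the Main Study. Its permission reads "Dose adjustments or switching from one medication to another within the same drug class are allowed after randomization for DPP-IV inhibitors", and it goes on to name SGLT2 inhibitors and GLP-1 agonists. Insulin is neither named nor prohibited there. Protocol 6.7 expressly allows one form of it: "Short-term use of sliding scale insulin therapy during a medical procedure or hospitalization (<5 days") in subjects with diabetes.

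**Measures.** Protocol 8.5.1.2 states that "HOMA-IR will be calculated by the central laboratory based on fasting glucose and insulin". Adipo-IR appears in the schedule (Protocol 1.3, Table 1) as "adipo-IR (fasting free fatty acids x fasting insulin"). SAP 4.1.6.1.4 and 4.2.4.2.3 list fasting insulin, HOMA-IR, Adipo-IR and C-peptide as exploratory laboratory parameters for the Main and Extension Studies.

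**Analysis.** SAP 7.8.3: "All other exploratory efficacy endpoints listed in Section 4.1.6 will be analyzed based on Full Analysis Set". The model is ANCOVA or MMRM, adjusted for the baseline value, T2DM status and fibrosis stage. SAP 7.12.3 summarizes the Extension exploratory endpoints on the Safety Analysis Set. Neither section mentions insulin use.

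**The concern.** HOMA-IR and Adipo-IR treat a high fasting insulin as the body's response to resistance. That interpretation weakens when some of the measured insulin may have been injected, because the reading then depends partly on the prescribed dose.

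Baseline insulin use should be roughly balanced by randomization, so the risk lies in what happens afterwards. If glycaemic control develops differently in the arms, insulin doses may too, and the plan has no means of separating a dosing change from a change in resistance.

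Insulin resistance is part of the drug's stated rationale (Protocol 2.1), and SAP 7.1 tests every comparison at 0.05 without multiplicity adjustment. A between-arm difference in these indices could therefore be read as mechanistic evidence.

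**Working it through.** The documents give no figure for this point, so there is none to reproduce. The check is to look for a safeguard and then to illustrate the size.

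**1. Is there a safeguard?**
- *Exclusion from the endpoint:* none in SAP 7.8.3 or 7.12.3.
- *Covariate:* T2DM status is in the model, but it separates diabetics from non-diabetics, not insulin users from other diabetics, and it carries no dose.
- *Subgroup:* SAP 4.3 lists T2DM but not insulin use, and applies to the primary endpoints.
- *Sampling conditions:* laboratory tests need a fast of at least 10 hours (Protocol 8.2.5). No insulin-free interval is set, and exclusion 28 leaves medication timing to the treating physician.
- *Alternative marker:* C-peptide is analysed separately and enters neither index.

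The plan does restrict on grounds of interpretability elsewhere. SAP 4.1.6.1.4 includes HbA1c change in subjects with baseline HbA1c of at least 6.5%. Protocol Table 1 limits LH, FSH and estradiol to women of childbearing potential not on hormonal contraception.

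**2. How do the indices respond?**
HOMA-IR = glucose (mg/dL) × insulin / 405, or glucose (mmol/L) × insulin / 22.5. The forms agree, since 22.5 × 18 = 405. At fixed glucose, HOMA-IR is proportional to measured insulin; at fixed free fatty acids, so is Adipo-IR. With an assumed glucose of 140 mg/dL:
- insulin 20 µIU/mL: 140 × 20 / 405 = 6.91
- insulin 30: 140 × 30 / 405 = 10.37 (+50%)
- insulin 10: 140 × 10 / 405 = 3.46 (−50%)

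The other factor may move the opposite way. If insulin rises from 20 to 30 while glucose falls to 120 mg/dL, HOMA-IR = 120 × 30 / 405 = 8.89, which is +29%. For Adipo-IR, a 50% rise in insulin with a 20% fall in free fatty acids gives 1.5 × 0.8 = 1.20, or +20%. The offset is partial in both examples.

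**3. What could this do to an arm mean?**
The share of insulin users, *f*, and the relative change in their measured insulin, *c*, are not in the documents. Both are assumed and shown as ranges. With no change in the other subjects and the second factor fixed, the shift in the arm-mean percent change is 100 × *f* × *c*:

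| Share on insulin | 25% change | 50% change |
|---|---|---|
| 5% | 1.25 points | 2.5 points |
| 10% | 2.5 | 5 |
| 20% | 5 | 10 |
| 30% | 7.5 | 15 |

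The sign follows the sign of the change. The between-arm difference moves by the same amount only if users in the other arm do not change. Equal changes in both arms, with equal shares of users, cancel.

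**The case against.** Three stronger readings are tempting, and the documents support none of them.

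*A reader might infer that the bias favours the drug.* That needs insulin doses to fall on pegozafermin, or rise on placebo, and the documents give no information on this. Less insulin also tends to raise glucose and free fatty acids, which offsets part of the change in the products. Neither direction nor size can be claimed.

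*A reader might infer that very high insulin values in users would greatly inflate the variance.* This would be true of raw insulin across subjects. The SAP models change from baseline with the baseline value as a covariate, which removes much of the stable difference between users and non-users. If model assumptions are severely violated, SAP 7.8.3 switches to a stratified van Elteren test, which limits the leverage of extreme values. Neither step removes a shift caused by dose changes that differ between arms.

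*A reader might take it as fact that injected insulin is measured.* The assay is not described, so this is an assumption. If the assay missed injected insulin, a dose change could still alter glucose, free fatty acids and the subject's own insulin, and the indices would remain hard to interpret.

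It is also fair to say that C-peptide is already planned and that these are only three exploratory parameters. Both points stand. They limit the importance of the gap but do not close it.

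**Conclusion.** The gap is real and minor. Insulin users are eligible, on-study insulin changes are not barred, all three measures use fasting insulin, and neither SAP section has a rule for these subjects. Followed as written, the plan can mix insulin dosing into a measure meant to show insulin resistance.

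The illustrative shift of about 1 to 15 points in an arm's mean percent change, in either direction, rests on three assumptions: 5% to 30% of the arm on insulin, a 25% to 50% change in their measured insulin, and the other factor in each index held constant. It describes what could happen and does not estimate what will. The primary, key secondary and other secondary results, the sample size and the error rate are untouched.

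**What to change.** State in SAP 7.8.3 (Full Analysis Set) and SAP 7.12.3 (Safety Analysis Set) that the main analysis of fasting insulin, HOMA-IR and Adipo-IR is in subjects not using exogenous insulin at baseline, identified from the concomitant-medication records. Each section keeps its own analysis set. Because the subset is defined by a baseline characteristic, the arms within it remain comparable.

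Keep the full-set analysis as supportive, in tables alongside the main one, so that the comparison in all subjects of the set is not lost.

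Add a sensitivity analysis that sets aside values after insulin is started on study, and say whether short-term sliding-scale use counts as a start. State its limit: it conditions on a post-randomization event that treatment may affect, and MMRM would treat the removed values as missing at random although insulin may have been started because control worsened.

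C-peptide is already planned for all subjects and can be read next to these results.

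The change needs a few SAP sentences. Protocol 6.7 already requires dates and dose for every medication, so no visit, sample or clinical rule changes. The downside is a smaller sample for three exploratory endpoints.

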2. INTRODUCTION

2.1. Study Rationale

BIO89-100 (hereafter referred to as pegozafermin), developed by 89bio, is a glycoPEGylated analogue of fibroblast growth factor 21 (FGF21), an endogenous metabolic hormone secreted by the liver, adipose tissue, skeletal muscle, and the pancreas, that is regulated by nutritional status and affects energy expenditure and glucose and lipid metabolism (Arner, 2008; Lee, 2014; Park, 2016).

In patients with nonalcoholic steatohepatitis (NASH), circulating and tissue levels of FGF21 are increased, correlate with disease severity, and are normalized by therapeutic interventions (Struik, 2019), indicating the presence of FGF21 resistance that is at least in part attributable to downregulation of fibroblast growth factor receptor (FGFR1) and β -Klotho expression in the liver (Oh, 2012).

Administration of exogenous FGF21 is being explored as a method to treat obesity-associated insulin-resistance disorders including NASH, the higher-risk variant of nonalcoholic fatty liver disease (NAFLD). There are currently no approved pharmaceutical treatments for NASH (Friedman, 2018). Several nonclinical and clinical studies have shown that administration of various FGF21 analogues had beneficial effects on serum lipids and insulin-resistance as well as on liver fat, liver enzymes and liver histology (Gaich, 2013; Zhang, 2014; Sanyal, 2019; Kaufman, 2020).

This randomized, double-blind, placebo-controlled Phase 2b study is designed to assess the efficacy, safety and tolerability of 3 dose regimens of pegozafermin (2 dose levels to be administered weekly [QW] and one dose level to be administered once every 2 weeks [Q2W]) in subjects with biopsy-confirmed NASH (NAFLD activity score [NAS] \geq 4, fibrosis stage F2 or F3 per NASH Clinical Research Network (CRN) system). The study will allow evaluation of the potential histological benefit of pegozafermin in the target population.

2.2. Background

NASH is a chronic liver disease, characterized histologically by \geq 5% hepatic steatosis, inflammation and hepatocellular injury (ballooning) (Chalasani, 2012). It is part of the spectrum of NAFLD, which is the most common chronic liver disease in North America and Europe. The NAFLD spectrum ranges from bland steatosis with or without inflammation (nonalcoholic fatty liver) to steatosis plus inflammation and hepatocellular injury, i.e., NASH, fibrosis and cirrhosis (Estes, 2018; Chen, 2020).

The pathophysiologic mechanisms that lead to NAFLD are thought to be similar to those in the development of type 2 diabetes mellitus (T2DM), as insulin resistance is a hallmark in both disease states. Insulin resistance in adipocytes leads to dysfunction in the normal regulators of lipolysis, contributing to elevated circulating free fatty acids, accumulation of triglycerides in the liver (Saponaro, 2015) and lipotoxicity, manifested as inflammation and cellular injury (Byrne, 2015). It is unclear why some patients with NAFLD do not progress to NASH; some genetic modifiers of disease progression and severity have been identified (including patatin-like phospholipase domain-containing 3 (PNPLA3) (Dongiovanni, 2013)). T2DM is associated with a greater than 2-fold increase in the risk of developing severe liver disease (Jarvis, 2020).

NAFLD is usually asymptomatic unless progression to cirrhosis has occurred. It is often diagnosed by demonstration of hepatic steatosis on liver imaging (e.g., ultrasound or magnetic resonance imaging [MRI]) in subjects, commonly with features of the metabolic syndrome (MetS), in whom no alternative etiology for liver fat accumulation can be identified (e.g., alcoholic liver disease, medications). A liver biopsy is the gold standard for assessing the presence of NASH and the presence of advanced fibrosis (the most important prognostic indicator in subjects with NAFLD) (Dulai, 2017; Balakrishnan, 2020); however, a number of non-invasive tools, e.g., clinical risk scores such as the NAFLD fibrosis score (NFS) and Fibrosis-4 (FIB-4) index, the enhanced liver fibrosis (ELF) score, and vibration-controlled transient elastography (VCTE), have been validated and are increasingly used in clinical settings for differentiation between subjects with a high vs. low risk of advanced fibrosis (EASL-EASD-EASO, 2016; Chalasani, 2018; Leoni, 2018).

The global prevalence of NAFLD in the general adult population has been estimated to be ~25% in a large meta-analysis of studies published through 2015 (Younossi 2016). The highest prevalence rates were reported in the Middle East and South America, and the lowest were in Africa. In North America and Europe, the prevalence of NAFLD is estimated at 21-25% (Younossi, 2016; Arshad, 2020; Mitra, 2020). The global prevalence of NASH has been estimated to range from 3% to 5% (Younossi, 2016; Younossi, 2018). The prevalence of NAFLD is on the rise (Younossi, 2016); in the US, the number of NAFLD cases is projected to expand from 83.1 million in 2015 (~25% of the population) to 100.9 million in 2030. An increased proportion of these cases will be NASH, rising from 20% to 27% of adults with NAFLD during this interval (Estes, 2018).

There is a high unmet medical need in NASH (Friedman, 2018). The disease progresses to fibrosis and cirrhosis in approximately 20% of affected patients (Vernon, 2011; Khan, 2015), and 45% of affected patients with cirrhosis will progress to decompensated cirrhosis within 10 years of diagnosis (Rinella, 2015). Eight percent of patients with advanced fibrosis will develop hepatocellular carcinoma within 5 years (Hashimoto, 2009), and there is increasing evidence that non-cirrhotic subjects with NAFLD may also be at an increased risk of hepatocellular carcinoma (Mittal, 2016). Moreover, NASH-related cirrhosis has become one of the leading causes of liver transplantation (Charlton, 2011; Golabi, 2018; Noureddin, 2018; Shingina, 2019).

As of this time, there are no approved therapies for treatment of patients with NASH (Attia, 2020). A variety of therapeutic agents are being developed for NASH, targeting metabolic pathways, inflammatory pathways or fibrosis (Attia, 2020; Dewidar, 2020; Dufour, 2020). Positive interim results (reduction of fibrosis) were reported from the ongoing REGENERATE Phase 3 study with obeticholic acid in patients with liver fibrosis due to NASH (Younossi, 2019a). In a Phase 2a proof-of-concept study, positive data were reported in NASH patients treated with pharmacological doses of FGF21 for 16 weeks with BMS-986036 (Sanyal, 2019; Verzijl, 2020). Furthermore, a beneficial effect of an Fc-FGF21 analog efruxifermin (AKR-001) was reported on key NASH parameters, e.g., reduction of liver fat and evaluation of histologic changes at 5 months in an ongoing study (BALANCED) in NASH patients (Akero Therapeutics Inc, 2020). In a Phase 1b/2a study (BIO89-100-002, Part 1), repeat administration of multiple

ascending doses of pegozafermin in subjects with NASH or phenotypic NASH (PNASH⁴) led to robust, significant, and clinically meaningful benefits across key liver parameters observed across all dose groups with concurrent metabolic benefits ([Loomba, 2020b](#)). Open-label, initial assessment of the effect of pegozafermin on histological endpoints in approximately 20 subjects with biopsy-proven NASH (F1 with high risk, F2 and F3) is ongoing (BIO89-100-002, Part 2).

